7.4 Evaluation at Completion of Study Intervention

Participants are to continue taking the study agent for the 90 day study period. All 90-day tests and procedures should take place as close to day 90 as possible, but may occur within 7 days of day 90 (from day 83-90) in order to accommodate participant conflicts and busy schedules.

Day 90 +/- 7 days

- Concomitant Medication Review
- Physical Exam and Vital Signs assessment – vital signs assessment is to include pulse, blood pressure, respiration rate, temperature and weight.
- UCDAI questionnaire to help assess disease state.
- Clinical Lab Tests (12-16 ml blood) – CBC, ESR, CRP, and Chemistry Panel (White blood count, RBC count, Hemoglobin, Hct, Platelets, Absolute Neutrophil Count, Glucose, Creatinine, Sodium, Potassium, Chloride, SGOT, SGPT, Total Bilirubin).
- Research blood will be collected: Peripheral blood for cytokines analysis (4ml in red top tube) and plasma for Berberine concentration analysis (5ml in purple EDTA tube).
- Colonoscopy with 7 biopsies from same region as, but ≥ 5 cm from, original biopsies taken at screening visit. If scars are visible from the site of screening biopsies, then new biopsies will be taken ≥ 5 cm from this site. If they are not visible, then biopsies will be taken ≥ 5 cm from the prior recorded distance (with the participant in the same position as they were in for original biopsies).
- Assess adverse events and review patient diary
- Collect and count study medication from patient

7.5 Post-intervention Follow-up Period

Participants will be assessed 30 days after their last dose of the study agent for assessment of adverse events (participants who experienced adverse events will be followed for 30days after their last dose or until all side effects have been resolved, whichever occurs later). For participants who completed the study this visit would occur on day 120.

Day 120 (+/-7 days)

- Physical Exam and Vital Signs assessment – vital signs assessment is to include pulse, blood pressure, respiration rate, temperature and weight
- Assess adverse events and discuss patient diary
- Assess Concomitant Medications

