5.1 Dose Regimen and Dose Groups

16 participants will be randomized into one of two groups: 12 participants will receive 300 mg Berberine three times per day; 4 participants will receive placebo tablets three times per day. Two additional participants (for a total of 18 participants) are anticipated to be enrolled to account for an anticipated dropout rate of 10%. In order to keep the numbers in either treatment group as planned (3:1), dropouts in either treatment group will be replaced by subjects assigned to that same treatment and gender group. Dosing will extend for 90 days.

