7. CLINICAL EVALUATIONS AND PROCEDURES

7.1 Schedule of Events

Evaluation/ Procedure	Screening	Randomization	Day 0*	Day 7 (+/- 3 days)	Day 30 (+/- 3 days)	Day 60 (+/- 7 days)	Day 90 (- 7 days)	Day 120 (+/- 7 days) or Early Termination
Informed Consent	X							
Assess Eligibility	X	X						
Medical History	X							
Physical Exam	X			X	X	X	X	
Vital Signs, Height and Weight ¹	X			X	X	X		X
Baseline Symptoms	X							
UCDAI Questionnaire	X					X		
Laboratory Tests ²	X					X		
Rectal Biopsy ³	X					X		
Research Blood Collection ⁴	X					X		
Concomitant Medications	X		X	X	X	X	X	X
Dispense Study Agent		X		X	X			
Pill Count				X	X	X	X	
Review Agent Diary/Record				X	X	X	X	
Adverse Events			X	X	X	X	X	X
Telephone Contact ⁵			X	X				
Collect Study Agent						X		

1. Vital signs assessment is to include pulse, blood pressure, respiration rate, temperature and weight. Baseline assessment must also include height.
2. CBC, ESR, CRP, and Chemistry Panel (White blood count, RBC count, Hemoglobin, Hct, Platelets, Absolute Neutrophil Count, Glucose, Creatinine, Sodium, Potassium, Chloride, SGOT, SGPT, Total Bilirubin, INR). Baseline assessment must include a serum pregnancy test for all women of childbearing potential. Pregnancy test will only be performed at the screening visit.
3. Colonoscopy with 7 biopsies from inflammatory loci (or from regions close to the initial inflammatory area when the patient was first diagnosed). Biopsies taken on day 90 should be ≥ 5 cm distance from the original biopsy sites.
4. Research blood collection: 5ml into purple EDTA tube for plasma and 4ml into red top tube for cytokines.
5. For Day 0, either a telephone contact or an office visit will occur.

* Participant should begin taking the study medication within 7 days of the screening visit

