8.2 Secondary Endpoints

Secondary endpoints will be evaluated in batch once the targeted number of study participants has completed the protocol.

- Clinical efficacy: Clinical efficacy will be measured using the UCDAI score^{13, 74}. This will be done at the screening visit and at the end of the trial (90 day-7days) by an endoscopist.

- Blood-based measures of inflammation: Biomarker analysis will be conducted using commercially available enzyme-linked immunosorbent assay (ELISA) kits for TNF α , IL-4, IL-6, IL-8 and IL-10 KIT (R&D Systems, Minneapolis, MN) according to the manufacturers' specifications. Other plasma-based measures of inflammation, including the blood CRP level and ESR will also be assessed.
- Tissue-based measures of inflammation and anti-cancer action: Inflammation-related biomarkers (TNF α , COX-2, and NF- κ B) and anti-cancer action biomarkers (Ki67 and activated caspase-3) in colorectal biopsy tissue will be evaluated by IHC and DNA methylation on SFRP1, TCERGIL FBN2, TFP12 using qMSP strategy.
- Histological analysis of inflammation: Histologic sections will be stained with H&E and the severity of histologic inflammation will be evaluated using the Geboes grading system^{25, 72}.
- Blood Berberine concentration measurement: Berberine concentrations will be measured using high-performance liquid chromatography /mass spectrometry (HPLC/MS).
- Blood Count and Blood Chemistry: Blood will also undergo standard clinical testing for complete blood count and blood chemistry to evaluate for end organ function.

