11.2.3 Follow-up of SAE

Site staff should send follow-up reports as requested when additional information is available. Additional information should be entered on the DCP SAE form in the appropriate format. Follow-up information should be sent to DCP and Lead Organization as soon as possible according to the DCP Serious Adverse Event Reporting Procedures and Guidelines. SAEs will be followed per protocol for 30 days after treatment completion or until all side effects have been resolved, whichever occurs later. As with the initial SAE report, follow-up SAE reports will be completed in Chinese and English. All follow-up SAE reports completed in Chinese will be translated into English then compared to the original English version to ensure accuracy.

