13.7 Evaluation of Toxicity

All participants will be evaluated for toxicity from the time of their first dose of Berberine through day 120 (corresponding to one month after completing the 90 day treatment period).

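### The Day 120 window lets the 30-day safety assessment fall 23 days after the last dose, and the end of safety observation for early stoppers is not reconciled

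*Combined protocol and SAP*

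**What the plan says.** Section 7.5 states: "Participants will be assessed 30 days after their last dose of the study agent for assessment of adverse events". For completers, it turns this 30-day assessment into a calendar day: "For participants who completed the study this visit would occur on day 120". The visit then carries a window of 7 days on each side. The last column of the 7.1 table is headed "Day 120 (+/- 7 days) or Early Termination" and gives no timing for the second case. Treatment length is set in 5.1: "Dosing will extend for 90 days".

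Section 13.7 says "All participants will be evaluated for toxicity from the time of their first dose of Berberine through day 120", and a parenthesis there equates Day 120 with one month after the 90-day course. Section 8.3 keeps people who stop the agent in follow-up on the schedule of events where possible. It follows those who stop for toxicity until the problem has settled or is stable.

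Events already known have their own rules. Section 7.5 follows participants with adverse events to the later of 30 days after last dose and resolution. Section 11.2.3 says "SAEs will be followed per protocol for 30 days after treatment completion or until all side effects have been resolved, whichever occurs later".

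The end-of-treatment window is stated in four places. The 7.4 heading allows 7 days on both sides of Day 90. The 7.4 text says procedures "may occur within 7 days of day 90 (from day 83-90"). The 7.1 table allows minus 7 days only. Section 8.2 times the UCDAI "at the end of the trial (90 day-7days").

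**The concern.** Safety is the primary endpoint. Section 13.4 classes each participant as having grade 2 systemic toxicity or not, and expects to see none. A zero-event result means little without a known period over which each participant could have registered an event. Here that period is stated as 30 days after dosing, but it is scheduled by calendar day with no minimum. For a participant who stops early, its end depends on which section the site follows. An event that first appears after an early final contact, but within 30 days of the last dose, would not be solicited at any scheduled contact.

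**Working it through.** **The plan's own figure.** Last dose on Day 90 (5.1) plus 30 days (7.5) gives 90 + 30 = Day 120. The nominal visit day is right.

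**Effect of the window.** Gap = follow-up visit day minus last-dose day. The Day 120 window runs from Day 113 to Day 127.

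| Last dose | Visit Day 113 | Visit Day 120 | Visit Day 127 |
|---|---|---|---|
| Day 83 (agent collected at an early Day 90 visit) | 30 | 37 | 44 |
| Day 89 (if Day 0 is the first dosing day) | 24 | 31 | 38 |
| Day 90 | 23 | 30 | 37 |

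The largest shortfall is 30 - 23 = 7 days. With a last dose on Day 83, even the earliest visit meets 30 days.

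**Early stoppers.** Two illustrative stopping days, with days since last dose in parentheses:

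| Rule | Last dose Day 30 | Last dose Day 60 |
|---|---|---|
| 7.5: last dose + 30 | Day 60 (30) | Day 90 (30) |
| 7.1, if the termination visit is the last contact | about Day 30 (about 0) | about Day 60 (about 0) |
| 13.7 read literally, or 8.3 with the schedule followed to its end | Day 120 (90) | Day 120 (60) |

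The middle row is one reading of an untimed label, not a stated rule. Section 8.3 does not settle the matter, because it refers back to the schedule that contains that label. Section 5.6 also describes stopping the drug as leaving the study, which does not sit easily with the continued follow-up in 8.3.

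**Who is affected.** Participants with a known adverse event or SAE, and those who stop for toxicity, are covered by 7.5, 11.2.3 and 8.3. The exposed group is participants with no known event at an early final contact. What can be missed is an event that starts afterwards.

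**Sensitivity of the primary result.** Section 13.4 gives a Rule of Three bound of 3/13 = 0.23 for the treatment group. The exact one-sided 95% upper bound for 0 of 12 is 1 - 0.05^(1/12) = 0.22. For 1 of 12 it solves (1 - p)^12 + 12p(1 - p)^11 = 0.05, which gives 0.34. One missed event would therefore matter. This says nothing about how likely a miss is, because the documents give no rate of late-onset events.

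**The case against.** A 7-day window around a nominal 30-day visit is ordinary practice and not an error in itself. The protocol also protects the people who matter most: anyone with a known event is followed for at least 30 days or to resolution, and toxicity stoppers until resolved or stable. Section 11.2.3 concerns SAEs that have already happened, so it is not a general promise of 30-day surveillance. The parenthesis in 13.7 ties Day 120 to completing the course, which agrees with 7.5, and follow-up to Day 120 can contain a visit at last dose plus 30. On that view the sections differ in clarity more than in substance.

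Most of this stands, and it limits the point to a shortfall of at most 7 days and to events not yet known at the final contact. It does not remove the point. Section 7.5 names 30 days without a minimum, and no section tells a site when an early stopper's last safety contact is due.

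A further fair objection is that ending the toxicity count at last dose plus 30 would itself create unequal observation. A participant stopping on Day 20 would be counted to 20 + 30 = Day 50 and a completer to Day 120, and data that 8.3 and 13.7 intend to collect could be dropped. The fix has to allow for this.

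The reference in 13.7 to a first dose of Berberine, which placebo participants never take, is a wording slip. The sentence opens with all participants, so its intent is clear.

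**Conclusion.** The point holds in a limited form. A completer with last dose on Day 90 and no known event can have the final contact 23 days after dosing, up to 7 days short of what 7.5 states. The end of safety observation for early stoppers is unreconciled across 7.1, 7.5, 8.3 and 13.7. The 23-day figure assumes dosing to Day 90 and a visit at the start of its window. The effect on the primary toxicity rate cannot be estimated from the documents.

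Three stronger readings are not supported:
- A reader might infer a gap of 16 days (113 - 97) from the two-sided 7.4 heading. That needs dosing to Day 97, beyond the stated 90-day course, and rests on one heading that the 7.4 text, 7.1 and 8.2 contradict. It is a contradiction to reconcile, not a second shortfall.
- A reader might infer that early stoppers get no follow-up after dosing. The 7.1 label can be read that way but does not require it, and 7.5 and 8.3 point the other way.
- A reader might infer that toxicity stoppers go unobserved. Section 8.3 gives an explicit rule for the event that led them to stop.

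**What to change.** - Schedule the final safety contact no earlier than 30 days after the actual last dose, for example with a window of 0 to +7 days, for every participant including early stoppers.
- Split the merged 7.1 column into an early-termination visit and a visit 30 days after last dose. Reconcile 5.6 and 8.3 on whether someone who stops the agent stays in follow-up.
- Reconcile the Day 90 window across the 7.4 heading, the 7.4 text, 7.1 and 8.2 into one statement.
- In 13.7, start toxicity evaluation at the first dose of study agent, Berberine or placebo. State one minimum window for the primary toxicity count, through at least 30 days after last dose, and still report all later events collected through Day 120.

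The cost is protocol wording and one schedule column for 16 to 18 participants. Early stoppers get a contact that 7.5 already describes. The downside is that final visits can no longer be held early.

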7.6 Methods for Clinical Procedures

Colonoscopies: The initial colonoscopy will be standard procedure. The colonoscopy at the end of the trial will be research colonoscopy. At the scheduled day, the patients will come to the endoscopy unit fasting after midnight. On the day prior to the exam, the patient will begin a clear liquid diet starting at lunch. The patient will then undergo a standard colonoscopy preparation with PEG. This prep is indicated for standard “GI lavage” and contains PEG-4000, sodium chloride, sodium bicarbonate and potassium chloride for oral solution. After informed consent, the participants will be placed on their left side and a rectal exam will be performed. Under conscious sedation, an Olympus video colonoscope will be inserted into the rectum and with minimal insufflation of air advanced to the cecum. At the beginning of the trial, 7 biopsies from inflammatory loci will be collected, if applicable. If no such loci are found, 7 biopsies close to initial inflammatory area (when the patients were first diagnosed) will be collected. The area of biopsy collection will be recorded by denoting the length in centimeters from the anal verge to the biopsy site as well as recording position of the participant during time of biopsy. At the end of trial (3 months later), 7 biopsies close to, but \geq 5 cm away from, this area will be collected. Six of these will be fixed in formalin and one will be flash frozen in liquid nitrogen. Specimen collection kits will be provided by the pathology department at Xijing Hospital. The study coordinator will arrange to have the biopsies processed for H& E sections by submitting to the study pathologists.

Research blood for drug concentration: 5ml blood will be collected (in purple-top EDTA tube) pre-dose (at the screening visit) and at 3 months after the start of dosing (at the Day 90 visit) for plasma drug concentration measurement. The clinical laboratory of Xijing hospital will provide specimen collection kits with all sample collection, labeling and packaging information. The research blood will be processed in the clinical laboratory of Xijing hospital. All samples will be logged in the lab logbook with the times of arrival to the lab. Plasma samples will be separated immediately by centrifugation at 4000 rpm for 3 min and stored at -80°C until analysis.

Research blood for cytokine levels: 4 ml of research blood (in red-top tube) will be collected at the pre-study screening visit and at the 3 month visit for cytokines level measurement. The clinical laboratory of Xijing hospital will provide specimen collection kits with all sample collection, labeling and packaging information. The research blood will be processed in the clinical laboratory of Xijing hospital. All samples will be logged in the lab logbook with the times of arrival to the lab. The blood samples will be spun down at 2500RPM for 10 min immediately upon arrival. Serum will be aliquoted before further detection and stored at -20°C until analysis.

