7.2 Baseline Testing/Prestudy Evaluation

Screening

- Informed Consent – written informed consent must be obtained prior to any other study procedure. Participants' signature is required on the research informed consent (in addition to the procedure consent) prior to undergoing the screening colonoscopy.
- Participants will be told not to take Berberine for 3 days prior to the screening biopsy.
- Medical History and Baseline Symptom Review.
- Concomitant Medication Review – all medications that the participant has taken within the 3 months prior to consent are to be recorded.
- Physical Exam and Vital Signs assessment – vital signs assessment is to include pulse, blood pressure, respiration rate, temperature and weight. Baseline assessment must also include height.
- UCDAI questionnaire to help assess disease state.
- Inclusion / Exclusion Criteria Review.
- Clinical Lab Tests (27-31 ml blood) CBC, ESR, CRP and Chemistry Panel (White blood count, RBC count, Hemoglobin, Hct, Platelets, Absolute Neutrophil Count, Glucose, Creatinine, Sodium, Potassium, Chloride, SGOT, SGPT, Total Bilirubin). Baseline assessment must include an INR for all patients and a serum pregnancy test for all women of childbearing potential. Women of childbearing potential include those who have not been surgically sterilized and have had a period in the past year. Screening labs must be completed within two weeks of registration.
- Research blood will be collected: Peripheral blood for cytokines analysis (4ml in red top tube) and plasma for Berberine concentration analysis (5ml in purple EDTA tube).
- Colonoscopy with 7 biopsies from inflammatory loci (or from regions close to the initial inflammatory area when the patient was first diagnosed). Each biopsy site will be recorded by denoting the length in centimeters from the anal verge to the biopsy site as well as recording position of the participant during time of biopsy (e.g., lying on their left side).
- Register the patient with Northwestern University Clinical Research Office.
- Provide agent diary (Appendix D) and review it with participant.

Randomization

- Confirm that the patient meets all inclusion/exclusion criteria.
- Randomize the patient with Northwestern University Clinical Research Office.
- Participant will be asked to return to the clinic within 6 days of the screening visit to pick up the study medication. Three (3) bottles 100mg x 120# Berberine tablets/placebo for use as medication will be dispensed.

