13.5 Secondary Objectives, Endpoints, Analysis Plans

Secondary Objectives: To determine the efficacy of Berberine and compliance of subjects.

Endpoints and Analyses:

- For plasma biomarkers, we will use descriptive statistics and graphical methods to present the evidence of possible correlations in outcomes of interest. Box plots and confidence intervals will be used to assign proper mass weight to groups of observations. “Before” and “after” intervention values and their difference will be compared with suitably chosen counterparts.
- Colorectal tissue IHC biomarkers and DNA methylation status for SFRP1, TCERGIL, FBN2 and TFP12 will be measured twice, before and after the treatment, and their difference will be studied in relative to values in their respective control groups. The Ki-67 and cleaved caspase 3 outcomes will be the number of cells positive over total number. The TNFa, COX-2, and NF- κ B immunohistochemistry will be done by quantitation through chromovision and will be expressed as % of control (placebo, pre-treatment). The description and comparison of biomarkers and gene methylation status will be performed both with the view of Before – After possible change within each treatment group, as well as with the view of Treatment - Control groups for Before and for the After period. Descriptive statistics and graphical methods will be performed to present the evidence of possible correlations in outcomes of interest. Tissue biomarkers will be measured in China and separately in the US. Comparisons of before and after treatment will be performed separately as a function of country, and then differences between countries will be compared. This will be done with the purpose of gaining knowledge of the range of changes to plan future studies in these markers.
- Blood drug concentration will be measured before and after 3 months treatment. Comparisons of before and after treatment will be performed.

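### Tissue inflammation markers can fall within an arm without a drug effect if inflamed sites are sought only at baseline; separately, 13.5 ranks no IHC estimate and leaves the baseline value unused

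*Combined protocol and SAP*

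**What the plan says.** **Where biopsies are taken.** Section 7.2 sets the screening procedure as "Colonoscopy with 7 biopsies from inflammatory loci (or from regions close to the initial inflammatory area when the patient was first diagnosed"). Section 7.6 ties this to the start of the study, "At the beginning of the trial, 7 biopsies from inflammatory loci will be collected, if applicable", with the area of first diagnosis as fallback. For the end of treatment, 7.4 asks for "Colonoscopy with 7 biopsies from same region as, but ≥ 5 cm from, original biopsies taken at screening visit", and 7.6 likewise gives only nearness and the 5 cm distance. Note 3 to the schedule in 7.1 belongs to the biopsy row, which covers both visits. It repeats the inflamed-site rule without limiting it to screening, then adds "Biopsies taken on day 90 should be ≥ 5 cm distance from the original biopsy sites".

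**How tissue markers are analysed.** Section 13.5 says of the before and after measurements that "their difference will be studied in relative to values in their respective control groups". It then describes comparisons with the view of "possible change within each treatment group, as well as with the view of Treatment - Control groups for Before and for the After period". TNF-alpha, COX-2 and NF-kB "will be expressed as % of control (placebo, pre-treatment"). Before/after comparisons are also made separately for the Chinese and US readings. On method it says: "Descriptive statistics and graphical methods will be performed to present the evidence of possible correlations in outcomes of interest". No estimate is named as the main one, and no adjustment for baseline is mentioned.

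**The concern.** Suppose the inflamed-site rule applies only at screening. A patient with a visible locus is then sampled first where the mucosa looks worst, and later at a site chosen by distance. The second sample will tend to look better even if nothing has changed. For the inflammation markers, that is the direction in which section 2.3 expects Berberine to act.

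Section 2.2 says the pilot biomarker data will support the design of later studies. In 13.5, the sentence about planning those studies directly follows the by-country before/after comparisons. A before/after fall carried forward as an expected drug effect would overstate it.

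A second, independent matter is efficiency. With 12 and 4 subjects precision is scarce, and 13.5 does not use each participant's baseline value to sharpen the arm comparison.

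**Working it through.** The plan gives no effect size, SD or error rate for the IHC markers, so it has no figure of its own to reproduce here. Arm sizes (12 and 4) are from 13.2. All other inputs below are assumptions.

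**1. Within-arm shift with no drug effect**

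Site values within a patient have SD 1.
- f: share of patients with a visible locus at baseline.
- k: number of candidate sites, of which the worst-looking is biopsied (2 to 5).
- r: correlation between visual choice and the marker.
- c: correlation between the Day 90 site and the baseline site.

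Mean fall = f × r × E[max of k] × (1 − c), where E[max] = 0.564, 0.846 and 1.163 for k = 2, 3 and 5.

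Examples: 0.25 × 1 × 1.163 × 1 = 0.29; 0.5 × 1 × 1.163 × 1 = 0.58; 0.25 × 0.5 × 0.564 × 0.5 = 0.04.

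| r, c | Fall, f = 0.25 | Fall, f = 0.5 | 95% CI excludes 0, f = 0.25 | 95% CI excludes 0, f = 0.5 |
|---|---|---|---|---|
| 1, 0 | 0.14-0.29 | 0.28-0.58 | 6-10% | 10-26% |
| 0.5, 0 | 0.07-0.15 | 0.14-0.29 | 5-6% | 6-10% |
| 0.5, 0.5 | 0.04-0.07 | 0.07-0.15 | 5-6% | 6-8% |

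Ranges run over k = 2 to 5, in within-patient site SD. The last two columns come from simulating a paired t interval in the 12-subject arm (60,000 trials per setting); the nominal rate is 5%. They are a yardstick only, since 13.5 plans no interval or test for tissue markers.

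A simpler model, in which a locus raises the marker by 0.5 to 1 SD and 0 to 50% of that persists at Day 90, gives falls of 0.06 to 0.75 SD for f = 0.25 to 0.75. It agrees on direction. The spread shows that the size is set by what is assumed.

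**2. Effect of the same shift on the arm comparison**

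Under six site-selection settings (12,000 trials each), the 12 v 4 interval excluded zero in 4.7-5.3% of trials for change scores, Day 90 values alone and baseline-adjusted values alike. The mean estimate was within 0.013 SD of zero. Randomisation gives both arms the same expected shift, so it cancels.

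**3. Precision of the arm comparison**

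Multiplier for 12 v 4: √(1/12 + 1/4) = 0.577. With t = 2.145 on 14 df and an average sample SD of 0.982 of the true SD, the mean half-width for Day 90 values alone is 2.145 × 0.577 × 0.982 = 1.22 total SD. For change scores, multiply by √(2(1 − ρ)), where ρ is the pre-post correlation. The adjusted figures are simulated.

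| ρ | Change score | Day 90 only | Adjusted | Narrower than change score | Narrower than Day 90 only |
|---|---|---|---|---|---|
| 0.3 | 1.44 | 1.22 | 1.21 | 16% | 0% |
| 0.5 | 1.22 | 1.22 | 1.10 | 10% | 10% |
| 0.7 | 0.94 | 1.22 | 0.91 | 4% | 25% |

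**Units.** The shift in step 1 is in within-patient site SD; the half-widths here are in total SD. With c = 0, the within-patient SD is √(1 − ρ) of the total. At ρ = 0.5 that is 0.71, so a shift of 0.58 becomes 0.58 × 0.71 = 0.41 total SD. The two sets of figures should not be compared without this conversion.

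**The case against.** A reader might infer that the plan lacks an unbiased tissue comparison, or that baseline adjustment is needed to remove a bias. The documents support neither. Section 13.5 opens its tissue analysis with change relative to control, which the site shift leaves unbiased (step 2). Adjustment buys precision only, so the two points must be kept apart.

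Other objections carry weight:
- Note 3 in 7.1 can be read as seeking inflamed sites at both visits. Selection would then be the same at each, and the shift would disappear.
- Section 9.1 links endoscopic appearance to histologic features, not to these IHC markers. That visual choice tracks them is plausible but assumed.
- A high f is unlikely. Section 4.1 requires UCDAI ≤ 1, so under Appendix A a scored locus is at most mild, with every other item at 0, including a global assessment that itself takes account of the endoscopic finding.
- Biopsies from one region are probably correlated, which makes c = 0 an extreme.
- Section 9.1 calls these endpoints exploratory, and 13.5 lists arm comparisons in the same bullet as the planning purpose. Use of the within-arm mean alone for planning is therefore an inference.

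These objections limit the size and weight of the point. They do not settle the Day 90 rule, and they do not tell the analyst which of several tissue summaries to rely on.

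**Conclusion.** Both points hold and are minor.

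1. If inflamed sites are sought only at baseline, the within-arm before/after views, the before/after comparison by country and any percent-of-pre-treatment scale can contain a fall that is not a drug effect. Under the assumptions shown, this is about 0.04 to 0.3 within-patient site SD at f = 0.25. It reaches 0.58 only at f = 0.5 with perfect visual selection and no correlation between sites. The documents give none of f, k, r or c, so these figures illustrate a range and do not estimate the shift.

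2. Independently, 13.5 ranks no IHC estimate and leaves the collected baseline value unused. At the correlations examined, adjusting for it gives an average interval no wider than either unadjusted arm comparison, and up to 25% narrower.

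The randomised contrast and the primary safety conclusion are unaffected. Nothing is claimed here about the Geboes grade or the methylation results.

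**What to change.** In 13.5:
- For the continuous IHC markers (TNF-alpha, COX-2, NF-kB, and percent positive for Ki-67 and cleaved caspase-3), make the main estimate the Berberine-minus-placebo difference at Day 90, adjusted for the participant's own baseline value, on the log scale where skewed, with a 95% CI.
- Report within-arm change, by-country before/after change and any percent-of-pre-treatment value as descriptive. State that they are neither evidence of a drug effect nor a measure of its size.
- Report by arm how many participants had an inflammatory locus at baseline.

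In 7.1 (note 3), 7.4 and 7.6, reconcile the text so that it is clear whether inflamed sites are sought at Day 90. Which rule applies is for the clinical team to state.

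**Cost.** A few sentences and one yes/no item at the screening colonoscopy, because the UCDAI endoscopic score is not specific to the biopsy site. No extra biopsies are needed. The changes can go into one amendment, which under 14.3 needs DCP and IRB/Ethics Committee approval. Adjustment spends one degree of freedom; adding gender, the stratification factor in 13.2, would widen the interval by about 1%. With 4 placebo subjects the half-width stays at about 0.9-1.2 total SD, so the estimate will rarely show an effect.
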